Demonstrating results are possible with 4 mA, which may be superior or unachievable with 2 mA, would persuade other researchers to also explore if the improvement (or the lack thereof) in their own tDCS studies would be present or larger using 4 mA tDCS. Over time, just as tDCS researchers began favouring 2 mA over lower intensity levels, 4 mA rather than 2 mA could become the new convention. Also, by exploring how individual differences impact the response observed, we can target those individuals who are expected to most benefit from tDCS. In this manner, tDCS studies can become more efficient.

[figure not shown]
Hypotheses Addressed

- The degree of improvement observed in people with Alzheimer's disease will be significantly greater when training is carried out at higher stimulation intensity (4mA vs. 2mA, SHAM).
- There will be significantly more significant improvement observed when:
 1. individuals have more atrophy (decreased brain volume, higher CSF volume).
 2. Individuals have a higher degree of impairment.
 3. The participant is female.

PRELIMINARY STUDIES

The proposed study models after our original three-round study [5] where three different tDCS montages were compared for improving naming ability. We recently completed another three-round study [31] where a mixed group of people with dementia (AD and FTD) concluded three consecutive rounds of executive function training with either: 4mA tDCS targeted towards the left dorsolateral prefrontal cortex (DLPFC), 2mA tDCS via two anode electrodes to the left and right DLPC respectively, or SHAM stimulation, which is the accepted placebo condition in tDCS studies. In SHAM stimulation, tDCS is only briefly active at the beginning and end of the session, which mimics the real-life sensation of tDCS as feelings are felt mainly only at the beginning and end of the session when the current is ramping up or down. We measured how much participants improved on an N-Back task, defined as having faster response times. For evaluation, participants completed two versions of this N-Back task: one practiced during the tDCS sessions, and another never practiced and was only given during evaluations. For trained items, results were similar regardless of stimulation condition, but the most significant improvement was found for the 4mA condition for untrained items.

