Because the bilateral montage delivered 2mA to each anode electrode over the left and right DLPC, finding superior results for the unilateral 4mA condition could be related to the involvement of the right DLPFC being stimulated, or due to a stronger intensity level being administered. The study proposed here will investigate the latter hypothesis: results were due to a more vigorous tDCS intensity (i.e., 4mA).

METHODS:

Sample

Based on pilot data, we expect a pooled standard deviation for response time on the N-Back test of 3,000 ms and a correlation of 0.89 between adjacent time points (pre, post, follow up). For 80% power to detect a difference across the three levels of intensity, while also accounting for the sex of a participant, a repeated-measures ANOVA test at an alpha level of 5% will require 54 participants with AD (27 men and 27 women). To compensate for anticipated attrition over the study, we will recruit a sample of 30 men and 30 women, 60 total, randomized into the three treatment arms. These participants would have received the diagnosis of probable AD from Baycrest's Memory Clinic expert staff [32, 33] according to standard clinical criteria. Only patients with no family history of epilepsy and who can give consent will be tested. We will seek people with mild to moderate AD (Reisberg stages 3, 4, or 5, [34]). Participants must show no history of stroke or traumatic brain injury, nor shunts or metal in the head that could interfere with the delivery of tDCS. Finally, people will have no evidence of significant heart disease, alcoholism, drug use. All

enrolled participants will be expected to complete an MRI; however, if they are unable to complete an MRI due to the presence of an exclusion criterion, they will still be allowed to complete all subsequent stages of the study. In the initial assessment, we will verify participants can complete the study task (N-Back). Only individuals able to complete this task will be allowed to complete the study.

Recruitment and Pre-Assessment

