Participants will be asked to arrive 15 minutes before their scheduled scan to review and fill the consent and MR screening forms. The participant will then be escorted to the Interview room to be interviewed by a Level 11 MR Personnel with respect to their MR screening form and medical history prior to changing for the MR exam. After changing, the MR technologist will escort the research participant into the magnet room and the accompanying researcher (Assistant, Coordinator or PI) to the control area. Post scanning, the lab member accompanying the research participant will monitor the change process, and other processes outlined in the “MR Research Suite Process Bacycrest – RRI.”

To be able to successfully perform the MRI, lab members will undergo the Virtual MR Safety Training & Orientation session and will also receive an in person suite tour.

Planned Analyses

The primary outcome measure will be improvement on an N-Back Task, both a trained version and an untrained version. Improvement will be measured in terms of the average response time (i.e., the amount of time needed to make a response). A repeated-measures ANOVA will be run to compare the three stimulation conditions (SHAM, 2mA, 4mA) with sex (male, female) as a between-subject variable. This analysis will be conducted separately for the trained and untrained items. Scheffé tests will compare the different conditions. We expect to find the greatest improvement in the 4mA condition.

Next, we will calculate a tDCS time improvement score for each participant per condition: the difference between the final average response time on the N-Back task from the last stimulation session subtracted from the baseline response time in each condition. To produce tDCS *effectiveness scores*, the time improvement score in the SHAM round will be deducted from the number calculated in each real tDCS round. In other words:

- Time Improvement in the 4mA condition *minus* Time improvement in the SHAM condition;
- Time Improvement in the 2mA condition *minus* Time improvement in the SHAM condition.

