If the event were to result in lasting pain and hospitalization, then it would be reported as a ‘Serious Adverse Event’ and full details would be noted to the research ethics board as well as Health Canada. These events would be recorded on the worksheets being used to collect the rest of the data. We must stress, however, that after administering 4 mA tDCS to around 60 participants, for hundreds of tDCS sessions, we have never encountered any such event. Although we have safety protocols in place for any encountered adverse or severe adverse events, we believe such events will fail to occur in the present study.

Confidentiality

A research study file as well as medical records identifying participants will be maintained within [name] lab. Names and identifying information will be replaced with a code, and the information will be kept on file for 10 years after the end of the study. Data collected from participants’ who withdraw from the study will also be kept, unless participants withdraw consent for its use.

Communication and Publication of Research Results

The found results may be presented at research conferences and written up in a manuscript submitted for a publication in a respected science journal. The data will never be used for commercial goals and all participant information will remain confidential. Individual’s participant data will be presented using a code (e.g., Participant 1), which ensures no reader of the data could identify the participant. The results found can also be used to back-up further studies involving 4 mA tDCS because

we will be able to present formal data demonstrating its effectiveness compared to other intensities of stimulation (SHAM, 2mA) in people with Alzheimer's Disease.

REFERENCES:

2. Zortea, M. et al. Transcranial Direct Stimulation to improve the dysfunction of descending pain modulatory system related to opioids in chronic non-cancer pain: An integrative review of neurobiology and meta-analysis. *Frontiers in Neuroscience*. 2019. 13(128)
3. [name], C., et al. tDCS stimulation alongside picture training improves naming scores in anomic dementia patients. in *Alzheimer's Association International Conference*. 2015. Washington.

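### The 80% power belongs to an overall three-condition F test, which does not test hypothesis 1 (4mA better than 2mA and SHAM), and no comparison is named as deciding it

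*Protocol*

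**What the plan says.** The first item under Hypotheses Addressed is comparative and directional. Improvement "will be significantly greater when training is carried out at higher stimulation intensity (4mA vs. 2mA, SHAM"). The section on communication and publication of results looks forward to "formal data demonstrating its effectiveness compared to other intensities of stimulation (SHAM, 2mA"). Both places set 4mA against two comparators.

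The Sample section sizes the trial on something else: "For 80% power to detect a difference across the three levels of intensity, while also accounting for the sex of a participant". The resulting number is 54, split equally by sex, with alpha set at 5%. The SD assumed for N-Back response time is 3,000 ms, and the only correlation stated concerns repeated measurements over time: "a correlation of 0.89 between adjacent time points (pre, post, follow up"). It gives no difference in milliseconds between any two conditions.

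Planned Analyses leads with the matching overall test: "A repeated-measures ANOVA will be run to compare the three stimulation conditions (SHAM, 2mA, 4mA) with sex (male, female) as a between-subject variable". The follow-up is described in one short sentence: "Scheffé tests will compare the different conditions". It also states an expectation that 4mA will show the greatest improvement. No section says which comparison, or which combination of them, decides hypothesis 1.

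**The concern.** An overall F test asks whether any of the three condition means differ, in any direction. Hypothesis 1 asks whether 4mA beats 2mA and also beats SHAM. The gap matters most for 4mA against 2mA, because the stated purpose is that 4mA might replace 2mA as the usual intensity.

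Suppose both active intensities beat SHAM by the same amount. The test on which the trial is sized would then tend to be positive, although raising the intensity gained nothing. The follow-up Scheffé tests could reveal this, but the plan does not say how a split result is read: F significant, 4mA better than SHAM, 4mA versus 2mA not shown. Nor does the 80% tell the reader how likely the trial is to establish its own hypothesis.

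**Working it through.** **Inputs from the protocol (Sample section).** N = 54 (27 men, 27 women), alpha 5%, power 80% for the overall test, SD 3,000 ms, correlation 0.89 between adjacent time points.

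**Assumptions made here.** One improvement score per person and condition; sphericity; two sex groups, so the error df are 2 × (54 − 2) = 104; a between-condition correlation of 0.89 wherever an effect is put in milliseconds, since the protocol gives no correlation between conditions.

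**Can the 54 be reproduced?** No, because no target difference is stated. With the above model and conventional f values of 0.10, 0.25 and 0.40, the condition effect needs 37, 8 and 8 participants (8 being the lowest number searched). The 54 is neither confirmed nor refuted. The check therefore works backwards from the plan's own 80%.

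**Step 1: noncentrality behind the 80%.** The critical F(2, 104) at 5% is 3.084. Power of 80% needs noncentrality λ = 9.92.

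**Step 2: what the overall test can tell apart.** λ = N × Σ(μ_j − mean)² / [SD² × (1 − ρ)].
- Only 4mA works, means (0, 0, d): the sum of squares is d² × (1/9 + 1/9 + 4/9) = (2/3)d².
- 4mA no better than 2mA, means (0, d, d): d² × (4/9 + 1/9 + 1/9) = (2/3)d².

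The two sums are equal, so the overall power is equal whatever the SD, the correlation or d. On the assumptions above, d = √[9.92 × 3,000² × 0.11 / (54 × 2/3)] = 522 ms gives 80% in both cases.

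**Step 3: the comparisons that hypothesis 1 needs.** The critical t for a Scheffé pair is √(2 × 3.084) = 2.483. For a planned contrast at two-sided 5% with 104 df it is 1.983. With each pattern scaled to λ = 9.92, a contrast has expected t of (difference in pattern units) × √[9.92 / (2 × SS)], where SS is the pattern's sum of squares.

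| Pattern (SHAM, 2mA, 4mA) | SS | Expected t, 4mA−2mA | Expected t, 4mA−SHAM |
|---|---|---|---|
| (0, 0, 1) | 0.667 | 2.73 | 2.73 |
| (0, 0.5, 1) | 0.500 | 1.57 | 3.15 |
| (0, 0.75, 1) | 0.542 | 0.76 | 3.03 |
| (0, 1, 1) | 0.667 | 0 | 2.73 |

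**Step 4: simulated results** (400,000 trials per pattern; success means significant and in favour of 4mA).

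| Pattern | Overall F | Both 4mA comparisons, Scheffé | Both, planned at two-sided 5% | Split result |
|---|---|---|---|---|
| Only 4mA works (0, 0, 1) | 80% | 44% | 65% | 16% |
| Equal steps (0, 0.5, 1) | 80% | 18% | 33% | 57% |
| (0, 0.75, 1) | 80% | 4% | 11% | 66% |
| 2mA = 4mA (0, 1, 1) | 80% | 0.7% | 2.5% | 59% |

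Split result means F significant, 4mA better than SHAM by Scheffé, and 4mA not shown better than 2mA. The 80% column is an input: every pattern was scaled to it. In the last row the two middle columns are false claims of superiority over 2mA.

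**Step 5: sensitivity.** The results in steps 3 and 4 depend on the shape of the pattern and on λ, so the assumed correlation affects only the conversion to milliseconds. If the SD and 0.89 describe pre and post scores, the SD of a change is 3,000 × √(2 × 0.11) = 1,407 ms. The d for (0, 0, d) then runs from 739 ms (between-condition correlation 0) to 330 ms (0.8).

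**The case against.** The strongest reply is that the plan already contains what is needed. The hypothesis names both comparators, Scheffé tests between conditions are prespecified, and the expected direction is stated. On the natural reading, a significant F without a 4mA advantage over 2mA fails hypothesis 1. This much stands: pairwise testing is not absent, and a reader who inferred that the protocol treats a significant F as confirming hypothesis 1 would go too far, since no section says so.

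A second reply is that naming the deciding contrast can be left to a statistical analysis plan, which may exist. That is fair for the naming alone. It does not remove the mismatch, because the hypothesis, the sizing target and the lead analysis are all fixed in the protocol and do not agree. On the natural reading, the 80% is the power of a different test.

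Third, the insensitivity shown in step 2 is a property of any overall F, and the equality is exact only for those two patterns at the same d. Both points are correct. They are reasons not to rest a hypothesis about 4mA on that test.

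Fourth, the Rationale argues that 2mA falls short of the field strength needed, which leans towards the pattern in which only 4mA works, the most favourable row. The same section also allows for people who improve at 2mA, so the other patterns cannot be set aside. Even the favourable row is well below 80% for both comparisons.

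**Conclusion.** The point holds as a mismatch between hypothesis and test. The 80% describes the overall three-condition test and not hypothesis 1, and none of the prespecified Scheffé comparisons is named as deciding. The equality in step 2 needs no assumption about effect size, SD or correlation.

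The power figures are illustrations. They rest on effects scaled to the plan's own 80%, one score per condition and sphericity. The only correlation stated is between time points, so the model that was actually powered may include time. A reader might infer that hypothesis 1 has a definite power of, say, one third to two thirds. The documents do not support that: with no target difference stated, the figure depends on the unknown dose pattern and falls to about 11% for (0, 0.75, 1), even with planned contrasts. Likewise the split result is common for graded or equal responses but occurs in only about 16% of trials if only 4mA works.

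Scheffé protects against every possible contrast and so costs power where only two are needed. Requiring two planned contrasts raises the chance of success from about 44% to 65%, or from 18% to 33%, while the false-superiority rate when 2mA equals 4mA stays near 2.5%.

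**What to change.** In Planned Analyses, state that hypothesis 1 is decided, within each item list, by two planned within-person contrasts from the repeated-measures model: 4mA minus 2mA and 4mA minus SHAM. Test each at two-sided 5%, report its 95% confidence interval, and require both to favour 4mA. Because both must succeed, no adjustment is needed across these two contrasts within one list. Having two primary lists, trained and untrained, is a separate issue that this change does not settle.

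Add that a significant overall F, or 4mA better than SHAM alone, does not show 4mA superior to 2mA. Treat the overall F and 2mA versus SHAM as supportive. Leave the sex hypothesis as it stands.

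In the Sample section, say that the 80% refers to the overall test only, and give the assumed condition means and the power of 4mA versus 2mA at N = 54.

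The cost is a few sentences and one power calculation, with no change to conduct. The downside is real: the power quoted for the actual hypothesis will be less favourable than 80%, and a significant F alone can no longer be reported as support. On the scaled effects above, 80% power for an unadjusted 4mA-versus-2mA contrast would need 58 participants if only 4mA works but 172 with equal steps. The sponsor should see that figure for its own assumed means before accepting 54.

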give sham or tDCS set at 2mA or 4mA for 20 minutes and will remain during the session with the participant for safety precautions and troubleshoot any computer problems. Simultaneously with the stimulation, participants will use the computer to practice the given N-back task. This N-back task is modeled off of the 1-back version of the N-back Matching Task [41]. In that study, participants were asked whether a presented digit (e.g., a red 5) was the same as the previously shown digit (either a red five or some other number-color combination); they gave their response by pressing a key on a keyboard to indicate if the number is the same (i.e., a red 5), or different (i.e., something other than a red 5). Following Basak and O'Connell [42], we have created different versions of this task but use images (animals, fruits, vehicles, faces) rather than numbers to make the task slightly easier for people living with dementia. The only difference between these versions is the stimuli presented. We also have normed these versions with normal elderly controls and found that response times and errors were similar for all versions. In each round, participants will practice a different version of the N-Back. Evaluations specific to that round will also administer a round-specific untrained list.

Subsequent Evaluations

For each round, in addition to the evaluation just before the first stimulation session, an additional evaluation will take place during the final training session, and two weeks later after the final session. In this manner, we can obtain a baseline measurement, check for post-stimulation changes, and if those changes have continued two-week's post-stimulation.

Structural MRI Protocol

Participants will undergo a Structural MRI at Baycrest. The protocol has been informed to the MR Technicians (please see attached documents). The Project Coordinator will book the MR suite using the Baycrest MR Web Scheduler with a 72 hour notice at the least.

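### Scheffé tests for three conditions are valid but inefficient: a gated overall test followed by pairwise tests is a cheap improvement, at a stated cost in error rate

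*Protocol*

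**What the plan says.** All references are to the Protocol.

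- **Planned Analyses**, main test: "A repeated-measures ANOVA will be run to compare the three stimulation conditions (SHAM, 2mA, 4mA) with sex (male, female) as a between-subject variable". It adds: "This analysis will be conducted separately for the trained and untrained items".
- **Planned Analyses**, follow-up: "Scheffé tests will compare the different conditions. We expect to find the greatest improvement in the 4mA condition". No other method for comparing conditions is named.
- **Planned Analyses**, after the ANOVA: a time improvement score per participant and condition, "the difference between the final average response time on the N-Back task from the last stimulation session subtracted from the baseline response time". It feeds the effectiveness scores and the regression. The text does not say that it is also the ANOVA variable.
- **Subsequent Evaluations**: besides the baseline of each round, "an additional evaluation will take place during the final training session, and two weeks later after the final session".
- **Hypotheses Addressed**: improvement will be "significantly greater when training is carried out at higher stimulation intensity (4mA vs. 2mA, SHAM").
- **Sample**: "For 80% power to detect a difference across the three levels of intensity", also allowing for sex, at alpha 5%, 54 participants are needed (27 men, 27 women) and 60 will be recruited. No effect size, pattern of means or power for any pair is given.

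**The concern.** Scheffé protects every contrast among the condition means, including many that nobody intends to test. With three conditions and three pairs, that protection is paid for in power on the pairs.

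A less costly valid route exists because there are exactly three conditions. Unless all three means are equal, at most one pair is truly null. A 5% overall test followed, only if significant, by unadjusted 5% pairwise tests therefore holds the family-wise error at 5% within each outcome.

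The comparison of 4mA with 2mA is part of the lead hypothesis and is what the trial is meant to inform. Scheffé makes it more likely that the overall test succeeds while this pair remains unproven.

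**Working it through.** **Inputs.** From the Protocol: three conditions, each received by every participant; 54 participants in two sex groups; alpha 5%; 80% power for the overall test. Assumed: one improvement score per condition, sphericity, two-sided pairs, and a pattern of means (SHAM, 2mA, 4mA) = (0, a, 1) × the 4mA effect, with a varied.

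**The Protocol's own figure.** The 54 cannot be reproduced forward, because no effect size is stated. It can be turned round: which effect gives 80% overall power at 54? Error df = (54 − 2) × 2 = 104 and F(0.95; 2, 104) = 3.084. Power of 80% needs noncentrality λ = 9.918. The rest depends only on λ and a, so the stated SD (3,000 ms) and correlation (0.89) do not enter.

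**Critical |t| for one pair (104 df).**
- Scheffé: √(2 × 3.084) = 2.483
- Bonferroni: 2.433
- Tukey (q/√2): 2.378
- Unadjusted: 1.983

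**Noncentrality for 4mA vs 2mA.** The squared deviations of (0, a, 1) sum to (2/3)(1 − a + a²), and the pair differs by 1 − a. Hence δ = √[0.75 λ (1 − a)² / (1 − a + a²)]. For a = 0, δ = √(0.75 × 9.918) = 2.73. For a = 0.5, δ = √(0.75 × 9.918 × 0.25/0.75) = 1.57.

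**Power for 4mA vs 2mA (%), pooled error, 400,000 simulated trials per row.** Gated means overall 5% test, then unadjusted 5% pair. Losses were computed before rounding.

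| a | δ | Scheffé | Tukey | Gated | Loss vs gated | Loss vs Tukey |
|---|---|---|---|---|---|---|
| 0 | 2.73 | 59.7 | 63.7 | 72.1 | 12.4 | 4.0 |
| 0.25 | 2.27 | 41.9 | 46.0 | 58.8 | 16.9 | 4.1 |
| 0.33 | 2.07 | 34.4 | 38.3 | 51.8 | 17.3 | 3.9 |
| 0.5 | 1.57 | 18.7 | 21.6 | 33.7 | 15.0 | 2.9 |
| 0.67 | 1.02 | 7.6 | 9.2 | 17.0 | 9.3 | 1.6 |
| 0.75 | 0.76 | 4.6 | 5.6 | 11.4 | 6.8 | 1.1 |

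The Scheffé and Tukey columns agree with the noncentral t distribution at these δ.

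**What the gain costs in error.** When only 4mA = 2mA is null, the error on that pair is P(|t| > critical value): Scheffé 1.5%, Tukey about 2%, gated 5.0%. Across two independent outcomes this becomes 1 − (1 − 0.0146)² = 2.9% for Scheffé and 1 − 0.95² = 9.8% for gated. With correlation between outcomes of 0, 0.5 and 0.8, simulation gives 2.9, 2.7 and 2.4% for Scheffé and 9.8, 9.1 and 7.9% for gated. Gated at 2.5% per outcome gives 4.9, 4.7 and 4.1%.

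**If all conditions are equal on both outcomes.** The chance of any false pair over the same correlations is 7.6, 7.1 and 6.2% for Scheffé, 9.4, 8.8 and 7.6% for gated at 5%, and 4.7, 4.4 and 3.9% for gated at 2.5%. Scheffé at 5% per outcome therefore does not hold 5% across outcomes either.

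**The wording proposed below** (Greenhouse-Geisser overall test, paired error terms; 200,000 simulated trials), power for 4mA vs 2mA (%):

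| 2mA share of 4mA effect | Scheffé 5% | Proposed 5% | Proposed 2.5% | Gain at 5% | Gain at 2.5% |
|---|---|---|---|---|---|
| none | 59.6 | 71.1 | 60.2 | 11.5 | 0.6 |
| one third | 34.0 | 50.5 | 38.8 | 16.5 | 4.8 |
| half | 18.8 | 33.1 | 23.3 | 14.3 | 4.5 |
| two thirds | 7.7 | 16.9 | 10.5 | 9.2 | 2.8 |

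**Why paired error terms.** With the 4mA variance tripled and 4mA = 2mA, error on that pair is 7.4% for the gated test with pooled error and 5.0% with the proposed wording (Scheffé 2.6%).

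**Sensitivity.** With N of 54 or 60, overall power of 70-90% and the four patterns in the last table, the gain over Scheffé is 8-18 points at 5% and −0.1 to 6.0 points at 2.5%. Tukey gains 1-4.

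**The case against.** The strongest reply is that nothing is broken. Scheffé is valid, pre-specified and conservative, and against Tukey, the ordinary alternative, it gives up only 1-4 points. That stands, and it is why this is an improvement and not an error. A reader might infer that the plan has an error-rate fault; the Protocol does not support that.

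Second, the larger gain is not free. A reader might take it as power recovered at no cost. Most of it comes from spending error on the 4mA vs 2mA pair that Scheffé leaves unused. Holding 5% across trained and untrained items leaves about 0-5 points. This also stands. The choice of overall level belongs to the trial team, since Planned Analyses sets none across the two outcomes.

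Third, the argument needs one score per condition. A reader might infer that the time improvement score is the ANOVA variable. Planned Analyses suggests this but does not state it, and the Sample section's correlation between pre, post and follow-up points towards time being in the model. A condition × time interaction with three evaluations has (3 − 1) × (3 − 1) = 4 df, and the three-means argument would not carry over directly. So naming the score is part of the change, not a detail.

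Fourth, the hypothesis can be read as 4mA against the other two together, a contrast that Scheffé covers. If only 4mA works, Scheffé's loss there is only about 5 points (74.5 vs 79.2%, pooled error). The proposed wording gives up cover for that contrast.

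What remains is that, with three means and pooled error, the gated procedure at 5% rejects a pair whenever Scheffé does and still holds 5% per outcome. With paired error terms the first part is nearly exact: it failed in at most 0.04% of runs.

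**Conclusion.** The point holds as a cheap improvement. Under the assumptions listed, Scheffé costs about 7-17 points of power for 4mA vs 2mA against the gated procedure at 5% per outcome, and about 1-4 against Tukey, when 2mA gives between none and three quarters of the 4mA effect. At 2.5% per outcome, power is about equal to Scheffé or up to about 5 points higher, with the false-claim rate on that pair at 4-5% across both outcomes.

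These sizes are conditional: the effect is back-solved from 80% overall power and the patterns are illustrations.

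A reader might also infer that the stated 80% applies to 4mA vs 2mA, or that changing the test cures low power on that pair. Neither is supported. The Sample section sizes the trial for the overall difference, and power for this pair stays below 80% in every pattern examined under every method.

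**What to change.** Before unblinding, replace the Scheffé sentence in Planned Analyses with:

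*For each outcome, the three conditions are compared on the time improvement score (baseline minus last stimulation session) with an overall test, Greenhouse-Geisser corrected; only if it is significant are 4mA vs 2mA, 4mA vs SHAM and 2mA vs SHAM each tested two-sided at the same level with its own paired error term; the level is 2.5% per outcome if 5% is to hold across trained and untrained items, otherwise 5%.*

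The final text should keep only the level chosen. No participants are added. The costs to record are:

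- Scheffé's simultaneous confidence intervals are lost, as is its cover for 4mA against the mean of the other two conditions.
- The score becomes the stated variable for these comparisons, so the two-week evaluation needs its own separate comparison.
- Paired error terms cost up to about 1 point of power under sphericity.
- At 5% per outcome, the error across the two outcomes rises as shown above.

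If simultaneous intervals are wanted, Tukey for the three pairs is the smaller alternative, worth 1-4 points.
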